**VERSION DATE:**

**12/8/2022**

**RELATED STUDIES:**

(STU00211218) This study has a similar experimental protocol, looking at the benefits of direct-to-consumer hearing aids for adults with hearing loss and mild cognitive impairment. The proposed study listed here will not include adults with cognitive impairment.

Check any **applicable** boxes in the table below – you will be asked for further detail on these topics later in the protocol form:

Indicate Vulnerable Populations to be enrolled:
 
 Children
 
 Cognitively Impaired Adults
 
 Pregnant Women (IF the research activities will affect the pregnancy or the fetus)
 
 Prisoners (or other detained/paroled individuals)

 International Research (check this box if you will collect data from individuals located outside the United States)

 Research involving external collaborators (some research activities will be carried out by individuals not employed by Northwestern or NU affiliates will carry out some research activities)

 Research has U.S. Federal government funding via one or more direct awards or a sub-award (i.e., NIH, NSF, other federal agencies or departments)

## 1.0 Purpose and rationale of the study:

Hearing loss is the third most common chronic health condition in the United States, affecting individuals of any age. According to the National Institute on Deafness and Other Communication Disorders approximately 15% of all adults over age 18 in the United States have reported some trouble with their hearing, and one in eight people in the United States (about 30 million) aged 12 and older have hearing loss in both ears. However, about 28.8 million US adults who could benefit from hearing aids do not wear them.

The current model of dispensing hearing aids could be a barrier to adoption by those who could benefit from amplification. For instance, the average cost of conventional hearing aids ranges from \$4000-5000 a pair, and this cost alone is often paid out of pocket due to limited insurance coverage for hearing care. Sound quality self-adjustments are highly restricted to the patient and vary based on manufacturer preferences and recommendations. Program changes are controlled by a licensed audiologist or hearing aid dispenser with the manufacturer’s software for sound quality adjustments. Also, appointments are common to fine-tune the hearing aids to meet the patient’s hearing needs, to replace the devices, or to repair them. These additional appointments are typically paid for out-of-pocket. The burden of upkeep, including not just the expense of office visits, but also the regular maintenance and care required for proper device functionality, may not only affect patients but their family members, loved ones, or caregivers. This is particularly true if transportation to and from appointments as well as if the availability of a caregiver or family member is limited. Thus, obtaining conventional hearing aids can carry with it the burden of affordability and reliance on the audiologist for regular maintenance. Mentioned are a few of many significant factors that could be contributing to the statistically low hearing aid adoption rates among adults who need them.

An alternative to conventional hearing aids, direct-to-consumer (DTC) hearing aids, have been

available for consumer purchase for years. Originally created as ‘self-fitting’ devices, these were marketed as personal sound amplification products, known as PSAPs. PSAPs were not meant to be used for hearing loss treatment, but rather more commonly as amplifiers for personal choice or recreational use such as for hunting. However, the Food and Drug Administration (FDA) issued a proposal in 2021 to make hearing care more accessible for Americans, known as the Over-the-Counter Hearing Aid Act, part of the FDA Reauthorization Act of 2017. Unlike PSAPs, DTC hearing aids in this Act would be considered a treatment option for hearing loss. Different from conventional hearing aids, these devices will not require appointments to an audiologist for adjustments. Due to their affordability and easy access, DTC hearing aids have the potential to reach more individuals with hearing loss. Despite the many potential benefits that DTC hearing aids could offer, there is little research into their use to meet unique patient listening needs and the accuracy of self-guided hearing aid fittings.

In order to better understand if DTC hearing aids may be a viable treatment option, it is important to consider patient reports. One of the most common complaints reported by patients is that listening is effortful, even when speech is loud enough. The Framework for Effortful Listening (FUEL) model developed by Pichora-Fuller and colleagues (2016), defines effortful listening as the “deliberate allocation of mental resources to overcome obstacles in goal pursuit when carrying out a task.” Research has shown that despite individualizing hearing aid programming to meet amplification targets as recommended by verification measures of output gain, audibility alone cannot resolve a damaged auditory system. Cognitive influence on auditory performance is an important consideration to hearing healthcare and the future of DTC devices. The complex process of comprehending and responding to incoming auditory stimuli requires intact cognition attuned to individual listening needs and differences. To the best of our knowledge, there exists a gap in research regarding cognitive processes involved in listening, particularly effort, with DTC hearing devices.

Currently available DTC and OTC devices that will be used for this study are listed here.

1. Bose SoundControl hearing aids: Currently listed within the U.S. Food and Drug Administration (FDA) as FDA cleared for regulatory class II as a self-fitting air conduction hearing aid in 2021.
2. Neosonic MX RIC-R hearing aids: Neosonic hearing aids been cleared and approved by the FDA as OTC hearing devices to treat mild to moderate hearing loss in adults over the age of 18 since 2022.
3. MDHearing Volt hearing aids: The MDHearing Volt has been cleared and approved by the FDA as medical devices to treat mild to moderate hearing loss in adults over the age of 18 since 2022.

## **2.0 Enrollment Criteria (who can be in your study and who would not be eligible to participate in your study):**

### **Inclusion criteria of participant:**

1. Adults ages 18-90 years
2. Speak English as their primary language
3. No vision impairment that would interfere with the ability to complete study tasks (i.e., legally blind, severe cataracts, or macular degeneration)

4. Bilateral mild to moderate sensorineural or mixed hearing loss
5. Pass a cognitive screener
6. Minimum Grade 10 education
7. Ability to attend all study visits

**Inclusion criteria of communication partner:**

8. Adults ages 18-90 years
9. Speak English as their primary language
10. No vision impairment that would interfere with the ability to complete study tasks (i.e., legally blind, severe cataracts, or macular degeneration)
11. Normal or corrected-to-normal hearing ability (i.e., use of hearing aids)
12. Pass a cognitive screener
13. Minimum Grade 10 education
14. Ability to attend all study visits

**Exclusion criteria of participant/communication partner:**

1. Clinically significant unstable or progressive medical conditions, or conditions which, in the opinion of the investigator(s) places the participant at unacceptable risk if he or she were to participate in the study
2. History of unresolved communication difficulties following another neurological problem (i.e., stroke or brain tumor), neurodevelopmental disorder (i.e., Down's syndrome), or head/neck cancer
3. Diagnosis of dementia or cognitive impairment
4. Positive history of major psychiatric disorder (i.e., schizophrenia, significant untreated depression)
5. Co-enrolled in other intervention studies targeting hearing, language, or communication strategies
6. History or current fluctuating hearing loss
7. Evidence of conductive hearing loss
8. Current active hearing aid wearer (defined as wearing hearing aid(s) at least 4 hours a day for most days within the past year)
9. Current active hearing aid wearer within 30-day trial period of purchased hearing aids from a licensed provider

For the purposes of test validation and calibration, we may also enroll a small group (n=10) of listeners with normal hearing, defined as pure-tone thresholds of 20 dB HL or less at octave frequencies between 250 and 4000 Hz. With the exception of having normal hearing, those participants will follow the inclusion and exclusion criteria described above.

We will not include any other special populations (adults unable to consent, individuals under 18 years of age, pregnant women, or prisoners or other detained individuals).

### **3.0 Sample Size:**

A study evaluating eye gaze and communication ability with hearing loss during the Diapix Conversation Analysis (Davis et al, 2017; DOI: [10.21437/AVSP.2017-3](https://doi.org/10.21437/AVSP.2017-3)), found a significant difference in their group of 19 dyads. Participants had hearing loss. To our knowledge, this is the only study with the most comparable methods to our study.

We will plan to collect data on 30 dyads (30 participants and 30 communication partners). We anticipate having 20 dyads by the end of our study, with 30 dyads set for room for dropouts. For visit 1 of the study, both parties will be required to attend the sessions. For visit 2, the communication partner does not need to attend. Historically less than 10% of participants drop out of studies within our lab. However, due to COVID19, we anticipate the possibility of higher-than-average dropouts.

The sample will consist of adults at least 18 years of age and older and their communication partner also be at least 18 years of age or older to participate.

#### **4.0 Recruitment and Screening Methods:**

Prior to scheduling any appointments, a brief phone screening will be conducted with the participant to obtain basic eligibility criteria (i.e., age, location, availability, language, current/previous hearing aid use). Prior to study enrollment, potential participants will agree to have their hearing and cognition completed with prior authorization via screening consent form. These preliminary screening tests will allow us to exclude ineligible participants from enrolling in the study.

Participants will be recruited from a variety of sources:

1. A within-laboratory participant pool of prospective participants that has been established by the primary investigator. Letters and emails will be sent to those who have previously agreed to be contacted for new studies.
2. Flyers and brochures posted around Northwestern University's campus, off-campus community bulletin boards, and relevant online community message boards (Nextdoor, Facebook).
3. Northwestern University Center for Audiology, Speech, Language, and Learning. Clinicians will receive a set of participant criteria. When possible, patients seen for clinic appointments that meet the criteria will be provided information about the study.
4. Postings to the investigators' websites and social media accounts.
5. Direct contact with persons interested in the study referred from outside sources.
6. Local senior and community activity centers, and local chapters of the Hearing Loss Association (HLAA).
7. Patient registries through the CNADS at Northwestern and the Communication Registry.
8. Local newspaper advertisements.

Participants who are interested in the study will contact the study coordinator via phone or email provided in the recruitment material. Prior to scheduling any appointments, a brief phone screening will be conducted to obtain basic eligibility criteria (i.e., age, location, availability, language, current/previous hearing aid use). Prior to study enrollment, potential participants will agree to have their hearing evaluated with prior authorization via screening consent form. These preliminary

screening tests will allow us to exclude ineligible participants from enrolling in the study.

## 5.0 Research Locations:

The main locations are Hearing Aid Lab spaces located in Frances Searle on Northwestern's Evanston Campus, private treatment rooms at Northwestern University Center for Audiology, Speech, Language, and Learning (NUCASLL); and the satellite School of Communication's research space located in Abbott Hall on Northwestern University's downtown campus. Data collection locations will be secured and kept in private, research-dedicated spaces that are accessed via key or keypad that are not accessible to the general public.

Some study visits may be conducted remotely via video conferencing software. Research staff will conduct these visits from a private space (in their home or in a research lab/clinic) that is secured from unintentional access by others not involved with the study. The virtual visits will be conducted through a School of Communication Information Technology-approved video-conferencing interface (i.e., WebEx, Zoom with password protection).

## 6.0 Multi-Site or Collaborative Research:

N/A

## 7.0 International Research (where data collection will occur outside the United States and U.S. territories, including online activities)

N/A

## 8.0 Procedures Involved:

Please check the boxes for all applicable data collection procedures you plan to use:

- One-on-one interviews
- Focus Groups
- Questionnaires/surveys
- Secondary Data Analysis (medical record data, educational records, government, or private sector datasets, etc.)
- Ethnographic observation
- Physiological measurements (i.e., EEG, EKG, MRI)
- Biospecimen collection (saliva samples, blood draws, hair samples, etc.)
- Mobile applications/data collection devices (i.e., Fitbits, actigraphs, etc.)
- Behavioral decision-making tasks (i.e., puzzles, interactive games, etc.)
- Physical activities such as walking and other forms of exercise
- Other procedures (briefly list types of procedures here if not covered by the check-boxes above):

\_Audiologic Assessment (hearing test and otoscopy), real ear measurement (hearing aid assessment)

**Approach:**

This is a within-subjects design and participants will wear hearing aids only during scheduled lab visits. Participants will **not** take the hearing aids outside the lab or home with them. The expected total duration of the study is 2-4 visits based on the typical timing of assessments and procedures. The range of duration of scheduling and visits will occur at times convenient for the participants. Although the study is sectioned into three visits (Eligibility, visit 1, and visit 2) participants can merge visits together (such as Eligibility and visit 1) into one visit, or split up a visit (i.e., such as changing visit 2 to two separate visits) based on the participant’s schedule and convenience.

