**Timeline**

---

**(1) Eligibility Screening: (Approximately 60-90 minutes, in person)** The Eligibility Screening will consist of inclusion questionnaires, communication questionnaires, and audiologic assessment. Both the participant and communication partner can be present for this visit and will both complete all testing for the Eligibility Screening.

If the participant and/or communication partner has had an audiologic assessment within the past year, then they are welcome to bring those results with them to their Eligibility Screening. If both the participant and communication partner have hearing assessment results from within the past year, then both of them will not be required to complete an audiologic assessment in the laboratory. If only one or neither member of the dyad has had an audiologic assessment within the past year, then the one member or both will complete an audiologic evaluation within the laboratory prior to visit 1.

Inclusion Questionnaires
	
Hearing health and history questionnaire: Participants will be asked questions regarding their hearing health history in an interview style format. If done remotely, this can be completed via phone or video chat.
 
MoCA: with a score <math>\geq 24</math> (within normal limits): The Montreal Cognitive assessment is a cognitive screening test designed to detect mild cognitive impairment. It requires approximately 10 minutes and assesses short-term recall, visuospatial abilities, executive function, attention, working memory, language, and orientation to time and place. This may be administered remotely via phone/video chat or in-person.
	
Data Collection Time: 20-30 minutes
	
Questionnaires have no risk involved for the participant

Communication
	
Communication Participation Item Bank
	
Data
	
Questionnaires

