
Diapix Conversation Analysis
	
Diapix Conversation Analysis: Consists of derived measures including proportion of trouble sources, proportion of unsuccessful repairs, proportion of complex repairs: video and audio recording will be collected from each participant/communication partner dyad at two timepoints: pre-fitting (unaided), and wearing the hearing aid (aided). Conversation data will be collected at one of our research sites, or remotely. If conversation data is collected in a participant's home or remotely, study staff will survey the environment removing (or positioning recording equipment to avoid recording) any personally identifying or sensitive information (i.e., mail with addresses, pictures of young children or unconsented individuals, personal
	
Data Collection Time: 70-90 minutes
	
Minimal to no risk: Minimal risk of boredom or minimal fatigue with task.
 
Participant is welcome to take a break at any time without consequence.

	
documents) prior to recording. If in person, the study team will replace these items once data have been collected as part of the session clean-up routine. Conversation data will be collected using standardized Diapix conversation tasks. The participant-communication partner pair will be seated approximately 3-5 feet apart with a barrier between them and will be instructed to describe standardized picture stimuli from to their partner (partner is not able to see the primary speaker’s picture but has a companion picture of their own). The goal of the conversation task is to have the partner use the primary speaker’s description to identify up to 12 objects that are missing on their picture, but present on the primary speaker’s picture. The Diapix sampling method is a standard approach for collecting conversation samples (Baker & Hazan, 2011). The Diapix pictures are freely available to the research and clinical community and can be found through the Northwestern Online Speech/Corpora Archive and Analysis Resource (OSCAAR; Kendall, 2010; http://oscaar.ling.northwestern.edu/).
		
--	--	--	--

**(3) Visit 2 (Approximately 60 minutes):** The second visit will consist of tasks of executive functioning (Stroop Task, Flanker Task) and a physiological measurement (pupillometry) to measure listening effort during the Rapid Recall Task (RRT). Only the participant will attend visit 2.

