
Pupillometry & Recall Repeat Task (RRT) (Data Collection Time: 30-40 minutes)
	
Pupillometry: a measurement of pupil size, is correlated with task difficulty in a variety of research focused on cognition. Task difficulty, or listening effort, during conversation is a useful measure of how effortful auditory processing is to the participant. The participant will be asked to rest their chin on a fixed chin rest and press their forehead on a cushioned support rest. Participant will be asked to fixate on a dot during the duration of testing. Testing will be completed with the Recall Repeat Task (RRT) during pupillometry recording. Pupillometry data collection will measure dilations of the pupil and record these dilations using EyeLink software.
 
Recall Repeat Task (RRT): an auditory only speech-in-noise task that assesses auditory
	
Data Collection Time: 30-40 minutes
	
Minimal risk to participants: Minimal to no risk include boredom with the task and minor fatigue from sitting still and maintaining a stable head position during the task. Participant is welcome to take a break at any time without consequence.

	
working memory and reported listening effort by participants. The participant is presented with a list of pre-recorded sentences that they are asked to repeat back and to recall 15 seconds after repeating back a list of 6 sentences. After the participant recalls the sentences heard, they are asked to rate on a scale of 1 to 10 how effortful they found the listening situation to be and are asked to provide an estimated time of how long they are willing to spend listening to speech-in-noise condition. Responses are recorded by the examiner in the testing interface, which is not visible to the participant.
		
--	---	--	--

For this study, we will not need to access any participant’s pre-existing HIPAA or PHI protected medical or health information or data. Also, we will not need to access any secondary data that is not HIPAA protection or contains PHI.

We will not use mobile apps for data collection during this study.

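### Visits may be split at convenience with no fixed break point, so a dyad's unaided and aided Diapix runs can fall on different days

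*Protocol*

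**What the plan says.** Protocol section 8.0, Approach, sets the design and the scheduling rule in one paragraph:

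- Design: "This is a within-subjects design and participants will wear hearing aids only during scheduled lab visits".
- Number of visits: "The expected total duration of the study is 2-4 visits based on the typical timing of assessments and procedures".
- Timing: "The range of duration of scheduling and visits will occur at times convenient for the participants". No interval or window is given.
- Flexibility: "participants can merge visits together (such as Eligibility and visit 1) into one visit, or split up a visit". The example of a split is "such as changing visit 2 to two separate visits". Both examples are illustrations and do not limit the permission.

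The Timeline names three visits: Eligibility, Visit 1 (fitting, verification and Diapix) and Visit 2 (Stroop and Flanker, then pupillometry during the recall task, RRT). The Diapix row fixes the order: one sample before the fitting without aids, and one while wearing them. That row also allows recording at a research site, remotely or at home. The Visit 1 text randomises testing with or without the audiologist-fit settings. It does not tie those conditions to one day.

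**The concern.** A within-person comparison is efficient because whatever is common to a person on a given day cancels from the difference. The scheduling rule lets that be lost without any deviation from the protocol.

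The clearest case is Diapix. If Visit 1 is broken between the unaided and aided runs, the first day is always unaided and the second always aided. The dyad's difference then contains the aid effect plus whatever changed between days, such as tiredness, recording set-up or setting. No analysis can separate the two within that dyad. The randomisation described for Visit 1 concerns the fitting settings, so it does not protect the unaided-aided contrast.

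The second case is weaker. Visit 2 measures listening effort, and the protocol neither fixes how much testing may come before it on the same day nor says that the RRT/pupillometry block must be done in one sitting. Who is tested in which state would depend on personal schedules.

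**Working it through.** **1. Stated durations (Protocol section 8.0, Timeline), in minutes**

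| Block | Stated | Sum of components |
|---|---|---|
| Eligibility | 60-90 | (20-30) + (30-40) + (15-20) = 65-90 |
| Visit 1 | 100-120 | fitting 15-30 + Diapix 70-90 = 85-120 |
| Visit 2 | about 60 | Stroop/Flanker 10-15 + RRT/pupillometry 30-40 = 40-55 |

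The components agree with the stated lengths apart from gaps of up to about 20 minutes, which changeover time could explain.

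**2. Do the problem schedules fit within 2-4 visits?**

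- Eligibility; Visit 1 first part; Visit 1 second part; Visit 2: four visits.
- Eligibility; Visit 1; Visit 2 first part; Visit 2 second part: four visits.
- Eligibility; Visits 1 and 2 merged: two visits.

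All three fit. Merging all three visits into one would not.

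**3. Effect of splitting the Diapix runs**

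Let s² be the within-day residual variance of one run and k·s² the between-day variance.

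- Same day: the day component cancels, and the variance of the difference is 2s².
- Different days: 2s² + 2k·s² = 2s²(1 + k).

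The protocol gives no k. For k = 0.25 to 1 (assumption) the factor is 1.25 to 2, so the SD of that dyad's difference rises by √1.25 = 1.12 to √2 = 1.41.

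If a fraction f of dyads is split, the average variance factor is 1 + f·k. As an illustration only, take a comparison with 80% power when every dyad is tested on one day (two-sided 5%, normal approximation; the protocol states neither alpha nor power). Power becomes Φ(2.80/√(1 + f·k) − 1.96):

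| f | k | 1 + f·k | Power |
|---|---|---|---|
| 0 | any | 1 | 80% |
| 0.25 | 0.25 | 1.0625 | 78% |
| 0.25 | 1 | 1.25 | 71% |
| 0.5 | 0.25 | 1.125 | 75% |
| 0.5 | 1 | 1.5 | 63% |

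This is variance alone. If the second day also shifts results by an average amount δ, the mean paired difference is biased by f·δ, because order is fixed. The documents give neither f nor δ.

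**4. Same-day testing before the effort block, in the listed order**

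- Effort block on its own day: 0 minutes.
- Visit 2 alone: 10-15 minutes.
- Visits 1 and 2 merged: (100-120) + (10-15) = 110-135 minutes (95-135 from component times).

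**The case against.** The harmful schedules are not the protocol's own examples. It names merging Eligibility with Visit 1, which leaves Visit 2 fresh, and splitting Visit 2, which has a natural break after Stroop and Flanker. Diapix is listed as one 70-90 minute block. Section 17.0 describes pupillometry as about 30 minutes with the head still, which reads as one sitting. These points make the harmful schedules less likely. They do not exclude them, because the permission is open-ended.

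A reader might infer that merging Visits 1 and 2 biases the effort comparison through fatigue. The documents do not support that:

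- If a participant's effort conditions share a session, earlier load is common to them and largely drops out of the contrast. What remains is spread between participants and a possible interaction with fatigue.
- The Visit 2 text does not say which hearing-aid conditions are compared. That is inferred from the Visit 1 text, which also supplies random allocation and so guards against systematic day or fatigue bias between the fittings.
- The fatigue statements are risk disclosures: "Minimal risk of boredom or minimal fatigue with task" for Diapix, and "minor fatigue from sitting still and maintaining a stable head position during the task" for pupillometry itself. Neither describes carry-over from Visit 1.

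It is also fair to say that unaided always precedes aided even within one day, so practice or tiredness within the session is already mixed with condition. Splitting adds day to that and does not create the order problem.

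The case against does not answer one point: nothing keeps the two Diapix runs, in their fixed order, on the same day.

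**Conclusion.** The point holds in a limited form. The scheduling rule, followed as written, can put a dyad's unaided and aided Diapix runs on different days. For that dyad, day and condition cannot be separated and between-day variance enters the difference. Section 3.0 expects about 20 dyads to finish, so there is little room for avoidable variance.

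The effort block is a secondary matter: it could be divided across days or done with very different amounts of earlier testing, mainly at the cost of between-person spread.

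The timing figures come from the protocol. The variance and power figures rest on assumed values of k and f, and f may turn out to be zero, so they show a range and are not an estimate for this trial. The point is a cheap improvement and not a demonstrated flaw.

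**What to change.** Replace the open permission in section 8.0, Approach, with these limits:

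- Eligibility may be merged with Visit 1. Both Diapix runs then share the same earlier testing.
- Visit 1 is not split between the unaided Diapix run, the fitting and the aided run or runs. All Diapix runs of a dyad take place on one day and in one setting, with the unaided run still before the fitting.
- Visit 2 may be split only between Stroop/Flanker and the RRT/pupillometry block. That block is done in one sitting and not on the same day after Visit 1.
- The date and start time of each block are recorded.

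A break in Visit 1 between the fitting and Diapix would not work. With all Diapix runs on one day, either the unaided run would follow the fitting, against the Diapix row, or no aided run would be possible. Allowing that break as well as a split Visit 2 and a separate Eligibility visit would also make five visits.

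Under the limits above the count is two (Eligibility with Visit 1, then Visit 2), three, or four (Visit 2 split), so the stated 2-4 stands. The cost is a few lines of text, a little recording and slightly less scheduling freedom.
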